Medical history and demographic data as collected in the parent Study WN29922 or WN39658 will be used in this study and should include clinically significant diseases, surgeries, cancer history (including prior cancer therapies and procedures), reproductive status, smoking history, and use of alcohol and drugs of abuse. Medical history and demographic data will be automatically transferred into the study WN42171 eCRF. In addition, ongoing concomitant medications will automatically be transferred from the parent study (WN29922 or WN39658) to study WN42171. All changes to medications during the study (e.g., prescription drugs, over the counter drugs, vaccines, herbal or homeopathic remedies, nutritional supplements) should be recorded in the eCRF. Changes in medical history will be collected once after completion of the double-blind part in the parent study (WN29922 or WN39658) and before OLE Day 1 either in the parent study or in study WN42171.

Demographic data will include age, sex, and self-reported race/ethnicity.

Because this study is being conducted in multiple geographic regions, it is likely that participants of different ethnic origins will be enrolled in the study. Although there is currently no indication that gantenerumab is metabolized or eliminated differently or that the treatment effect would be different in participants of different ethnic origins, collecting this information is essential to adequately evaluate the results of this study (e.g., possible differences in PK exposure [concentration of the drug in the blood] or treatment effect).

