4.5.4 Physical Examinations

A complete physical examination, performed at specified visits as per the schedule of activities (Appendix 1), should include an evaluation of the head, eyes, ears, nose, and throat, and the cardiovascular, dermatologic, musculoskeletal, respiratory, gastrointestinal, and neurologic systems; genitourinary examinations may be performed if clinically indicated. Conditions reported as part of the medical history or adverse events in the parent study do not need to be re-entered.

Limited, symptom-directed physical examinations should be performed at specified visits and as clinically indicated. Changes from baseline abnormalities should be recorded in participant notes. New or worsened clinically significant abnormalities should be recorded as adverse events on the Adverse Event eCRF.

In addition, weight will be obtained at OLE Day 1, at OLE Week 104, *at OLE Week 208*, or at the OLE early termination visit, at every visit at which creatinine clearance is tested, and at any other visit as deemed necessary by the investigator. Height will be obtained at the first dosing visit only.

The physical examination does not have to be repeated at OLE Day 1 or at the first dosing visit in the WN42171 study if the last examination performed in the parent study (WN29922 or WN39658) occurred within the previous 4 weeks.

4.5.5 Vital Signs

Vital signs will include measurements of respiratory rate, pulse rate, systolic and diastolic blood pressure while the participant is in a seated position, and temperature. Any abnormalities recorded in the parent studies do not need to be re-entered on the Study WN42171 eCRF. At subsequent visits, record new or worsened clinically significant abnormalities on the Adverse Event eCRF.

Blood pressure and pulse rate should be taken when the participant is at rest and should not be measured unless at least 15 minutes have elapsed since the last blood draw. The same arm should be used for all blood pressure measurements.

Pulse rate will be determined and will be recorded as beats per minute. If obtained manually, the pulse rate should be counted for a minimum of 20 seconds at each assessment.

Vital sign measurements may be performed by an MN professional.

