6.4 SAFETY ANALYSES

The safety analysis population will include all enrolled participants who received at least one dose of study drug in this protocol.

The following safety outcome measures will be summarized using descriptive statistics:

- Nature, frequency, severity, timing, and outcomes of adverse events and serious adverse events
- Physical examinations (including neurological systems), vital signs, ECG, laboratory tests, and C-SSRS
- Nature, frequency, severity, and timing of ARIA-E and ARIA-H
- Nature, frequency, severity, timing, and outcomes of injection-site reactions
- Incidence of treatment discontinuations for adverse events
- Incidence of adverse events of special interest

Statistical methods, endpoint definitions, and analyses of the safety endpoints will be described in a SAP.

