#### 5.3 PRIMARY ENDPOINTS ANALYSIS

### 5.3.1 Definition of Primary Endpoints

The primary objective for this study is to evaluate the safety and tolerability of long-term gantenerumab administered by SC injection on the basis of adverse events (AEs), physical examinations, vital signs, ECGs, laboratory tests, C-SSRS, ARIA-E and ARIA-H, ISRs, treatment discontinuations for AEs, and incidence of AEs of special interest.

The corresponding primary endpoints are:

- Nature, frequency, severity, timing, and outcomes of adverse events and serious adverse events
- Physical examinations (including neurologic systems), vital signs, ECG, laboratory tests, and Columbia-Suicide Severity Rating Scale (C-SSRS)
- Nature, frequency, severity, and timing of ARIA-E and ARIA-H

- Nature, frequency, severity, timing, and outcomes of ISRs
- Incidence of treatment discontinuations for adverse events
- Incidence of adverse events of special interest

The analytical approaches are described in pertinent subsection for each endpoint below.

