### 5.3.3 Adverse Events

All verbatim AE terms will be coded using the Medical Dictionary for Regulatory Activities (MedDRA) version that is current at the time of the analysis (Version 25.0 or higher), and AE severity will be graded according to the scale defined in Table 3 in Section 5.3.3 of the study protocol (mild/moderate/severe). For each displayed participant group, the frequency of each AE preferred term will be defined as the number of participants experiencing at least one occurrence of the event. Each table will present the overall number and percentage of participants experiencing at least one AE and the total number of AEs reported. Percentages will be based on the number of participants in the SE analysis set. In summary tables, AEs will be sorted by body system (in decreasing order of overall incidence), then by preferred term (in decreasing order of overall incidence). The summary tables will be restricted to treatment-emergent AEs, i.e., AEs that occur or worsen on or after the day of first OLE dose, with onset no later than 14 weeks after last dose. Non-treatment-emergent AEs (AEs ongoing at OLE Day 1 with onset before the first OLE dose) and AEs occurring more than 14 weeks after the last dose will be listed.

The following safety information will be summarized:

- AEs, AEs by intensity, AEs related to study drug
- AEs with fatal outcome

- Serious AEs (SAEs), SAEs by intensity, SAEs related to study drug
- AEs leading to discontinuation of study treatment
- AEs leading to dose modifications (dose interruption, dose reduction, or delayed uptitration). Delayed up-titration at any given visit is defined as the simultaneous occurrence of the following two tickboxes in the eCRF Adverse Event form:
  - Action taken with open label gantenerumab due to SAE/AE: Dose Not Changed
  - If Dose not changed, was open label dose regimen modified from protocol schedule due to SAE/AE? Yes
- Injection site reaction (ISR) signs and symptoms
- Systemic injection reactions (AEs with "systemic reaction" selected)

Protocol-specified adverse events of special interest (AESI) will be listed.

The impact of the COVID-19 pandemic on the safety data will be assessed by reviewing the following:

- Confirmed or suspected COVID-19 AEs
- AEs associated with COVID-19
- Potential long COVID-19 symptoms

The following data handling rules will be applied for all AE summary tables:

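### Outcomes of AEs, SAEs and injection-site reactions belong to the primary endpoints, but SAP 5.3.3 plans only fatal AEs and no ISR outcome, and Appendix 1 does not declare the omission

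*SAP*

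**What the plan says.** SAP 5.3.1 lists six primary endpoints, in line with Protocol 2.1.1. Two of them name outcomes: "Nature, frequency, severity, timing, and outcomes of adverse events and serious adverse events" and "Nature, frequency, severity, timing, and outcomes of ISRs". SAP 5.3.1 then refers the reader to the subsections that follow for the analysis of each endpoint.

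Protocol 6.4 makes the commitment: "The following safety outcome measures will be summarized using descriptive statistics". The list after that sentence includes the AE/SAE endpoint and "Nature, frequency, severity, timing, and outcomes of injection-site reactions". The section leaves the methods to the SAP.

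SAP 5.3.3 is where the AE outputs are specified. Its list contains AEs overall, by intensity and by relatedness; "AEs with fatal outcome"; "Serious AEs (SAEs), SAEs by intensity, SAEs related to study drug"; AEs leading to discontinuation or dose modification; ISR signs and symptoms; and systemic injection reactions.

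SAP Appendix 1 records changes from the protocol. It covers the data scope, the descriptive nature of the analyses and the absence of estimands. It does not mention outcomes of AEs or ISRs.

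**The concern.** A primary endpoint component should lead to at least one specified output. Here outcome is promised in the protocol and repeated in the SAP's endpoint list, and it then disappears from the outputs except for death. SAP Section 1 states that the SAP's language supersedes the protocol's, so the promise in Protocol 6.4 does not by itself restore the missing tables.

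At stake is part of what a long-term safety study is meant to show: whether events resolve. This matters most for ISRs, one of the two identified risks. Protocol 1.3.2.2 reports them in 36% to 38% of patients in the two earlier OLE studies, all non-serious and mostly resolving untreated. For such events a table of fatal outcomes says almost nothing, and resolution is the outcome of interest. SAP 5.8.1 takes the AE content of the planned interim analyses from Section 5.3.3, so the gap would also reach the outputs meant to support a potential filing.

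**Working it through.** No sample size, error rate or event count is involved. The check sets the endpoints against the outputs and then follows an AE that is ongoing at rollover.

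**Endpoints against outputs**

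| Endpoint (SAP 5.3.1) | Outcome named? | Outcome output in SAP 5.3.3 |
|---|---|---|
| AEs and SAEs | Yes | Fatal AEs only |
| Physical examination, vital signs, ECG, laboratory, C-SSRS | No | – |
| ARIA-E and ARIA-H | No | – |
| ISRs | Yes | None specific to ISRs; signs and symptoms only |
| Discontinuations for AEs | No | – |
| AEs of special interest | No | – |

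Two of six endpoints name outcomes. Against them SAP 5.3.3 has one outcome summary (fatal AEs), no summary of non-fatal outcome for AEs or SAEs, and no ISR outcome summary. The fatal table would include a fatal SAE, so SAEs are covered to that extent.

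**Are the data there?** Protocol 5.5.1 has each AE followed to resolution or a stable state, with resolution dates entered on the AE eCRF. Under Protocol 5.3.5.1 the ISR diagnosis is itself an AE eCRF record; only the signs and symptoms go on a separate form. The SAP 5.3.3 rules for incomplete dates already refer to end dates, unresolved events and duration. The summaries therefore need no new data collection.

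**AEs ongoing at rollover**

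1. Protocol 5.3.1 assigns an event to the parent or the WN42171 AE eCRF according to when it occurs.
2. Protocol 4.5.4, on physical examinations, says: "Conditions reported as part of the medical history or adverse events in the parent study do not need to be re-entered".
3. Protocol 4.5.3 says that medical history and demographics are transferred automatically, and that "ongoing concomitant medications will automatically be transferred from the parent study (WN29922 or WN39658) to study WN42171". It is silent on AEs.
4. Protocol 5.5.1 continues follow-up and the recording of resolution, but does not say on which study's AE eCRF.
5. SAP 5.1 brings parent-OLE data into this study's report, and SAP 5.3.3 lists AEs ongoing at OLE Day 1. Both presuppose that parent AE records are available.

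Together these passages leave one thing open: which eCRF holds the later outcome of an event that began in the parent study. The question matters mainly for participants from the parent OLE, whose events starting after the first OLE dose count as treatment-emergent and enter the summary tables.

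**The case against.** The best defence is that the SAP already covers outcome in general terms. SAP 5.3.2 commits to descriptive statistics for all safety data, table layouts are left to the Data Analysis Plan, deaths are tabulated, resolution data are collected, and nothing is tested. Part of this stands. The study is descriptive, so no estimate or test is damaged, and an outcome column could well appear in a listing. The rest does not close the gap. SAP 5.3.2 sends the reader to the later sections for the content of the summaries, and those sections omit outcome. SAP Section 1 gives the Data Analysis Plan layouts, datasets, programs and the linking of outputs to the report, not the choice of primary-endpoint analyses.

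A reader might infer something stronger: that AEs ongoing at rollover are neither transferred nor re-entered, that their outcome therefore stays fixed at the last parent visit, and that unresolved events would be overstated for participants from the parent OLE. The documents do not support this. Non-transfer is inferred only from silence in Protocol 4.5.3. Not re-entering an event fits the rule in Protocol 5.3.5.5 that a persistent AE is recorded once. Protocol 5.5.1 requires follow-up with no stop at rollover, and SAP 5.1 and 5.3.3 rely on parent records. The supposed bias would also need an outcome table that is not planned, and the number of affected events is not given.

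**Conclusion.** The coverage gap holds. If SAP 5.3.3 is carried out as written, outcome goes unsummarised for non-fatal AEs and SAEs, and no ISR outcome is summarised, although two of the six primary endpoints name it. Because Appendix 1 does not declare the omission, a reader cannot tell whether it was intended. This is more than a missing detail, since a stated part of the primary endpoint would go unreported, but it distorts no result that is planned.

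The conclusion assumes that SAP 5.3.3 is the governing list of AE outputs, as SAP 5.3.1 and 5.3.2 indicate, and that no document outside the protocol and SAP adds the tables. On rollover, the documents show only that the place for recording a later outcome is unspecified.

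**What to change.** In SAP 5.3.3, add descriptive summaries of outcome for treatment-emergent AEs, for SAEs and for ISRs, in the same columns as the other AE tables: previous treatment, participation or not in the parent OLE, and overall. Use the outcome and resolution data already recorded on the AE eCRF. Take the categories from the form's own outcome field, which the documents do not show. State how a participant with several occurrences is counted, as the section already does for intensity.

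As a clarification only, add a sentence saying which study's AE eCRF holds the later outcome of an AE ongoing at rollover, and that the summaries use that source.

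The cost is a few extra tables and their programming. No new data collection, eCRF redesign or change to treatment rules is needed, and the SAP change can be made on its own.

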4.3.2 Study Treatment Dosage, Administration, and Compliance

During the WN42171 study, participants previously randomized to the active treatment arm and those who were previously randomized to placebo and have completed OLE uptitration in the parent study (WN29922 or WN39658) will continue to be administered the study drug every 2 weeks (Q2W administration of 510 mg SC gantenerumab). Participants previously randomized to the placebo arm who did not participate in the OLE part of the parent study (WN29922 or WN39658) will be required to undergo the uptitration scheme of 34 weeks. Participants who completed the OLE part of the parent study (WN29922 or WN39658), will continue the schedule of activities as per their OLE Day 1 visit in the parent study (WN29922 or WN39658).

In order to maintain the previous study treatment blinding (the Sponsor, investigator, and participant), all participants will be dosed every 2 weeks as illustrated in Table 1. A safety MRI should be performed before each uptitration to ensure the participant can be safely uptitrated to the next dose.

To ensure blinding to previous treatment, IMP will be administered as one 0.8-mL and two 1.7-mL injections for the 120-mg dose or as two 1.7-mL injections for the 255-mg dose and 510-mg dose, respectively, SC to the abdomen. Injections may contain active gantenerumab or placebo to ensure the correct total dose of active gantenerumab at each visit (see Table 1). Refer to the pharmacy manual for detailed instructions on drug preparation, storage, and administration.

Note: A minimum of 3 doses during each dosing step must be administered before the participant is eligible for uptitration, subject to the results of a pre-uptitration safety MRI. **A dose is defined as two consecutive dosing visits (one with an odd dose number and one with an even dose number,** see Table 1). A participant may still be eligible for uptitration even if these requirements are not met, provided that they have been administered IMP at 3 odd dosing visits at a given dose level (see Table 1).

Gantenerumab—F. Hoffmann-La Roche Ltd 46/Protocol WN42171, Version 4

After OLE Week 34 (i.e., beyond the time frame considered in Table 1), all participants who have completed the uptitration will receive two 1.7-mL injections of active gantenerumab for the 510-mg dose at each subsequent 2-week visit.

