5.3.5.2 ARIA Findings

Not every ARIA finding qualifies as an adverse event. An ARIA finding must be reported as an adverse event if it meets any of the following criteria:

- Symptomatic ARIA-E (onset or worsening of CNS symptom[s] attributable to ARIA-E MRI findings in the judgement of the investigator)
- ARIA findings that result in a change in study treatment (e.g., dosage modification, treatment interruption, or treatment discontinuation)
- Findings that are otherwise clinically significant in the investigator's judgment

Any accompanying symptom(s) should also be captured as separate adverse events. It is the investigator's responsibility to review all ARIA findings. Observations of the same clinically significant ARIA finding should only be recorded once on the Adverse Event eCRF (see Section 5.3.5.5 for details on recording persistent adverse events).

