Aβ = amyloid beta; ADA = anti-drug antibody; ADAS-Cog13 = Alzheimer's Disease Assessment Scale–Cognition, Subscale 13; ADCS-ADL = Alzheimer's Disease Cooperative Study Group–Activities of Daily Living; ARIA-E = amyloid-related imaging abnormality–edema/effusion; ARIA-H = amyloid-related imaging abnormality–microhemorrhage/hemosiderin deposition; BL = baseline; CDR = Clinical Dementia Rating; CSF = cerebrospinal fluid; C-SSRS = Columbia–Suicide Severity Rating Scale; DTI = diffusion tensor imaging; eCRF=electronic Case Report Form; EQ-5D = EuroQol 5-Dimension Questionnaire; FAQ = Functional Activities Questionnaire; MMSE = Mini-Mental State Examination; MRI = magnetic resonance imaging; NPI-Q = Neuropsychiatric Inventory Questionnaire; OLE = open-label extension; PK = pharmacokinetic; Q2W = every 2 weeks; QoL–AD = Quality of Life–Alzheimer's Disease; RUD-Lite = Resource Utilization in Dementia–Lite; SLV = since last visit; T4 = thyroxine; UV = unscheduled visit; ZCI-AD = Zarit Caregiver Interview for Alzheimer's Disease. B = before study drug administration; CG = caregiver completion; P = participant completion; P&CG = participant and caregiver completion. Notes: The participant, the site, and the Sponsor will be kept blinded to the dose level given in order to keep the previous treatment assignment blinded. The visit window is ±3 days and +3 days for OLE non-dosing Day 4. It is recommended that not more than 2 dosing visits are given (i.e., 2×510 mg Q2W) within 28 days. Participants should return to initial planned schedule per baseline visit (OLE Day 1) for subsequent visits.

- ^a The relevant assessments will be determined by the Principal Investigator per clinical judgment, not necessary to include all assessments listed above. An additional plasma and RNA blood sample for the assessment of exploratory biomarkers will be obtained as soon as practicable (e.g., at an unscheduled visit or the next study visit) following each MRI scan showing ARIA-E until and including ARIA-E resolution (i.e., new, worsened, stable, improved, resolved ARIA-E); following new or worsened ARIA-E.

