Appendix 2 Management Rules for Amyloid-Related Imaging Abnormalities

Event	Characteristic	Action to Be Taken
ARIA-E	Asymptomatic and mild (Bioclinica severity 1)	 Continue study drug according to the schedule of administration (including uptitration). Perform MRI scans at 4-week intervals until ARIA-E resolves. Then, resume the standard MRI schedule.
	Asymptomatic and mild +	
	Asymptomatic and mild + (Bioclinica severity 2) or moderate (Bioclinica severity 3)	 During uptitration period: Continue study drug at the same dose level and do not uptitrate. Perform MRI scans at 4-week intervals until ARIA-E resolves. Once ARIA-E resolves, continue uptitration and resume the standard MRI schedule.
		 During treatment period (at target dose): Continue study drug according to the schedule of administration. Perform MRI scans at 4-week intervals until ARIA-E resolves. Then, resume the standard MRI schedule.
	Asymptomatic and moderate +	During uptitration period:
	(Bioclinica severity 4) or severe (Bioclinica severity 5) Or Symptomatic ARIA-E ^a of any	 Temporarily interrupt study drug. Perform MRI scans at 4-week intervals until ARIA-E (and any ARIA-E symptom/s) resolves.
	severity (Bioclinica severity 1–5)	 Once ARIA-E (and any ARIA-E symptom/s) resolves, reintroduce study drug at the dose level given at the time the event was detected.
		Perform an MRI scan after two consecutive dosing visits.
		 If no new ARIA-E is detected, continue uptitration and resume the standard MRI schedule.
		During treatment period (at target dose):
		Temporarily interrupt study drug.
		 Perform MRI scans at 4-week intervals until ARIA-E (and any ARIA-E symptom/s) resolves.
		 Once ARIA-E (and any ARIA-E symptom/s) resolves, reintroduce study drug.
		 Perform an MRI scan after two consecutive dosing visits.
		 If no new ARIA-E is detected, resume the standard MRI schedule.
	Any recurrence of ARIA-E	• Treat as above.

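### SAP 5.3.3 counts a masked titration hold in a prior-active participant as delayed uptitration, although no increase in active drug was delayed

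*SAP*

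**What the plan says.** **SAP 5.3.3.** AEs leading to dose modification comprise three kinds: interruption, reduction and delayed uptitration. The third is derived from the AE form: "Delayed up-titration at any given visit is defined as the simultaneous occurrence of the following two tickboxes in the eCRF Adverse Event form". The boxes are "Action taken with open label gantenerumab due to SAE/AE: Dose Not Changed" and "If Dose not changed, was open label dose regimen modified from protocol schedule due to SAE/AE? Yes". The data-handling rules later in the section do not restrict this by previous treatment, dose step or week.

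**Protocol 4.3.2 and its Table 1.** To preserve the parent-study blind, "all participants will be dosed every 2 weeks as illustrated in Table 1". In that table, prior-placebo participants step through 120, 255 and 510 mg every 4 weeks, with placebo visits in between. Prior-active participants have 510 mg every 2 weeks at each of the 18 visits from OLE Day 1 to Week 34.

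**Protocol Appendix 1, Table 1 notes.** "The participant, the site, and the Sponsor will be kept blinded to the dose level given".

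**Protocol 5.1.2.1 and Appendix 2.** Everyone who did not enter the parent OLE has an MRI before each step. For asymptomatic ARIA-E of Bioclinica severity 2 or 3 during uptitration, the instruction is "Continue study drug at the same dose level and do not uptitrate". Neither place distinguishes the previous arms.

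**SAP 5.1, 5.3.2 and 5.8.1.** Safety results are shown by treatment actually received in the parent study, by parent-OLE participation, and overall. AE summaries also enter the planned interim analyses.

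**The concern.** The table is about AEs that changed gantenerumab dosing. For a prior-active participant in the masked titration, holding the next step changes nothing active. The blinded site cannot know this. It follows the same MRI and hold rules as for anyone else and can truthfully tick both boxes. The SAP rule then converts the site's record into a delayed uptitration.

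Two displays would then disagree. The exposure summary by dose level (SAP 5.6.1) would place these participants at 510 mg from the start, while the AE table would say that uptitration was delayed. A reader comparing prior-active with prior-placebo columns, or using the overall column in an interim report for a filing, would take a feature of the blinding for a treatment effect on dosing.

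**Working it through.** The point concerns a derivation rule, so the plan has no power, alpha or event figure to reproduce. The check is whether a hold alters the active drug delivered.

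**Inputs (protocol 4.3.2 and Table 1).** A 0.8 mL active injection carries 120 mg and a 1.7 mL active injection 255 mg. Both are 150 mg/mL (120/0.8 = 255/1.7 = 150), so two 1.7 mL injections give 510 mg.

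**Active drug to Week 34 without a hold**
- Prior placebo: 3 × 120 + 3 × 255 + 3 × 510 = 2655 mg.
- Prior active: 18 × 510 = 9180 mg.

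**With one 4-week hold.** The length is assumed: two extra visits at the held step, matching the 4-week MRI interval in Appendix 2, and counting only the same 18 visits.

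| Held step | Prior placebo | Prior active |
|---|---|---|
| 120 mg | 4 × 120 + 3 × 255 + 2 × 510 = 2265 mg | 18 × 510 = 9180 mg |
| 255 mg | 3 × 120 + 4 × 255 + 2 × 510 = 2400 mg | 18 × 510 = 9180 mg |

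The hold costs a prior-placebo participant 390 mg (2655 − 2265) or 255 mg (2655 − 2400). It costs a prior-active participant nothing. At the 120-mg step the only effect for the latter is that the 0.8 mL placebo injection continues for longer. At the 255-mg step even the injections are identical before and after.

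**Tracing one case through the rule**
1. A prior-active participant who skipped the parent OLE has asymptomatic severity 2 ARIA-E on a pre-uptitration MRI.
2. Under Appendix 2 the site continues dosing and does not uptitrate.
3. If the site regards this as a change in study treatment (protocol 5.3.5.2), or the finding as clinically significant, it reports an AE.
4. It ticks dose not changed, and regimen modified from schedule.
5. SAP 5.3.3 counts the AE as delayed uptitration, and so as leading to dose modification.

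**Size.** The documents give no hold rates. For illustration only, take equal numbers of prior-placebo and prior-active participants titrated in this study, with hold rates p and a:
- Rate as written: (p + a)/2.
- Rate limited to real titration: p/2.
- Share of counted delays that are masked holds: a/(p + a).

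With p from 5% to 15% and a from 1% to 5%, the rate as written runs from 3.0% to 10.0% and the limited rate from 2.5% to 7.5%. The masked share runs from 1/(15 + 1) = 6% to 5/(5 + 5) = 50%. The rates are assumptions; the range shows only that the share depends on a figure that the documents do not supply.

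**The case against.** The best defence is that the table records what blinded investigators did, which is a legitimate descriptive summary, and that a footnote would be enough. Several facts also limit the harm:

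- ARIA incidence, severity and timing come mainly from MRI findings (SAP 5.3.4), which a tickbox cannot alter.
- Columns are split by previous treatment and OLE participation, so the entries sit where they can be found.
- Nothing is tested (SAP 2). Treatment discontinuations for AEs are a named primary endpoint; dose modifications are not.
- The affected group had already reached 510 mg every 2 weeks and had no ARIA-E on the last parent-study MRI (protocol 4.1.1, 4.1.2). ARIA tends to come early in treatment (protocol 1.3.2.1). Before Week 36 the scheduled on-treatment scans are at Weeks 12 and 24 only.

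All of this stands as a limit on size. It does not rescue the rule. A footnote would leave masked holds inside the total, and the overall column has no split to protect it.

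Four stronger readings are tempting, and the documents do not support them.

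- *Every delayed-uptitration entry in a prior-active column is false.* The second tickbox asks about any departure from schedule, so a postponed dose at an unchanged 510 mg might be ticked the same way. Also, placebo-randomised participants who received any active double-blind dose are shown as active (SAP 4), yet their titration may be real.
- *The prior-active ARIA AE rate will seem to fall after Week 34.* No AE comparison before and after that week is planned.
- *All asymptomatic severity 2–3 findings become AEs during masked titration and none do afterwards.* That bounds a single reporting criterion. Protocol 5.3.5.2 does not name delayed uptitration among its examples, and clinically significant findings are reportable in either period.
- *Any AE triggers the Appendix 2 hold.* Appendix 2 covers ARIA only. Severity 1 without symptoms continues to uptitrate; severity 4–5 or symptomatic ARIA-E is a real interruption in either arm.

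**Conclusion.** The point holds for one component of one descriptive safety table. As written, the rule counts masked holds as delayed uptitration in the prior-active column for participants who skipped the parent OLE, and in the overall column. The direction is certain for any such hold that is recorded with both boxes ticked: it adds to the count without any change in active dose. The size is unknown and probably small.

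This rests on sites applying the hold rule alike in both arms. Protocol 4.2.1 and 4.3.2 describe the 34-week titration as applying to prior-placebo participants, but a site blinded to dose level cannot confine the procedure to them. The eCRF completion guidance is not among the documents and could affect how often both boxes are ticked. No hypothesis test, sample size or MRI-based ARIA result changes. The correction is still worth making, because the rule as stated misclassifies events and the data to correct it are already needed elsewhere in the SAP.

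**What to change.** Amend the derivation in SAP 5.3.3:

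1. Count delayed uptitration only when dosing or IxRS records show that a scheduled increase in active gantenerumab was held. Use those records, not the previous-treatment column label, so that placebo-randomised participants displayed as active are classified by the titration they really had.
2. Put all other entries with both boxes ticked on a separate line: regimen modified, active dose level unchanged.
3. Within that line, separate masked-titration holds, which leave the dose-modification total, from genuine schedule changes such as postponed doses, which stay in it.
4. Leave interruptions and discontinuations counted as they are now.

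Flagging ARIA AEs that were reported only because of a masked hold is optional.

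The cost is a few lines of SAP text and one extra merge. The dosing data are already needed for exposure by dose level (SAP 5.6.1) and ARIA by dose level (SAP 5.3.4), and the parent studies are to be unblinded while this study is running. The prior-active dose-modification count will be lower. No dosing or clinical rule changes.
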